3.14.1.2. Common Adverse Events

The counts and percentages of participants with TEAEs, overall and common (common TEAEs occurred in \geq 5% of participants before rounding), will be summarized by treatment using MedDRA PT. Events will be ordered by decreasing frequency in the tirzepatide arm.

3.14.1.3. Deaths

A listing of all deaths during Study GPID will be provided. The listing will include participant identification including the treatment, site number, date of death, age at the time of enrollment, sex, associated AE group identification, time from last dose of study drug to death (if participant had discontinued study drug), and primary cause of death.

3.14.1.4. Other Serious Adverse Events

The counts and percentages of participants who experienced an SAE (including deaths and SAEs temporally associated or preceding deaths) during the postbaseline period will be summarized by treatment using the MedDRA PT nested within SOC. Events will be ordered by decreasing frequency in the tirzepatide arm within SOC. The SOC will be in alphabetical order.

A listing of all SAEs will be provided. The listing will include treatment, participant identification including the site number, date of event, age at the time of enrollment, sex, AE group identification, MedDRA SOC and PT, severity, outcome, relationship to study drug, time from first dose of study drug to the event, and time from most recent dose to event (if the participant discontinued study drug prior to the event).

3.14.1.5. Other Significant Adverse Events

The counts and percentages of participants who discontinued from study treatment or study due to an AE during the postbaseline period may be summarized by treatment group using the MedDRA PT nested within the SOC. Events will be ordered by decreasing frequency in the

tirzepatide arm within SOC. Additionally, a Kaplan-Meier plot of time to study treatment discontinuation due to AEs will be presented.

3.14.2. Patient Narratives

Patient narratives will be provided for all participants who experience any of the following "notable" events:

- death
- protocol defined serious adverse event,
- pregnancy, or
- permanent discontinuation of study treatment due to AEs.

Patient narratives (patient level data and summary paragraph) will be provided for participants in the randomized population with at least 1 notable event.

3.14.3. Special Safety Topics

For AE(s) of special interest (AESI) or special safety topics, the counts and percentages of participants will be summarized by treatment and PT with decreasing frequency in the tirzepatide arm. Individual participant-level data may be presented. Displays with individual participant level data may be created using various formats, such as a customized listing and/or a customized graphical participant profile. AESI are defined in each section of the special safety topics, where applicable.

3.14.3.1. Amputation/Peripheral Revascularization

Amputation/peripheral revascularization will be considered as AESI. Participants with amputations/peripheral revascularization will be searched using the following MedDRA PTs and summarized:

- Amputation, and
- Peripheral revascularization.

A listing of participants with treatment-emergent (TE) events will be provided.

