8.3.3. Adverse Events of Special Interest

The following are AESI and will be adjudicated by an external adjudication committee. This committee will be blinded to treatment assignment.

- pancreatitis
- major adverse CV events (see Section 10.5.1.5), and
- deaths

The following are additional AESI for this program that will not be adjudicated by an external committee:

- hepatobiliary disorders
- severe hypoglycemia
- thyroid malignancies and C-cell hyperplasia
- supraventricular arrhythmias and cardiac conduction disorders
- allergic/hypersensitivity reactions, including injection site reactions and ADA formation
- severe GI AEs, and
- acute renal events.

Sites should collect additional details and data regarding AESI, as instructed on the applicable eCRFs, and detailed in Section 10.5.

The details on the definition of AESI will be provided in SAP.

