- Any clinically significant abnormal laboratory findings or other abnormal safety assessments which are associated with the underlying disease, unless judged by the investigator to be more severe than expected for the participant's condition.
- The disease/disorder being studied or expected progression, signs, or symptoms of the disease/disorder being studied, unless more severe than expected for the participant's condition.
- Medical or surgical procedure (for example, endoscopy, appendectomy): the condition that leads to the procedure is the AE.
- Situations in which an untoward medical occurrence did not occur (social and/or convenience admission to a hospital).
- Anticipated day-to-day fluctuations of preexisting disease(s) or condition(s) present or detected at the start of the study that do not worsen.

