10.3.2. Definition of SAE

If an event is not an AE per the definition above, then it cannot be an SAE even if serious conditions are met (for example, hospitalization for signs/symptoms of the disease under study, death due to progression of disease).

SAE is defined as any untoward medical occurrence that, at any dose:

a. Results in death

b. Is life-threatening

The term "life-threatening" in the definition of "serious" refers to an event in which the participant was at risk of death at the time of the event. It does not refer to an event, which hypothetically might have caused death, if it were more severe.

c. Requires inpatient hospitalization or prolongation of existing hospitalization

- In general, hospitalization signifies that the participant has been admitted to the hospital for observation and/or treatment that would not have been appropriate in the physician's office or outpatient setting. Complications that occur during hospitalization are AEs. If a complication prolongs hospitalization or fulfills any other serious criteria, the event is serious. When in doubt as to whether "hospitalization" occurred or was necessary, the AE should be considered serious.
- Hospitalization for elective treatment of a preexisting condition that did not worsen from baseline is not considered an AE.

d. Results in persistent disability/incapacity

• The term disability means a substantial disruption of a person's ability to conduct normal life functions.

• This definition is not intended to include experiences of relatively minor medical significance such as uncomplicated headache, nausea, vomiting, diarrhea, influenza, and accidental trauma (for example, sprained ankle) which may interfere with or prevent everyday life functions but do not constitute a substantial disruption.

e. Is a congenital anomaly/birth defect

• Abnormal pregnancy outcomes (for example, spontaneous abortion, fetal death, stillbirth, congenital anomalies, ectopic pregnancy) are considered SAEs.

f. Other situations:

- Medical or scientific judgment should be exercised in deciding whether SAE reporting
 is appropriate in other situations such as important medical events that may not be
 immediately life-threatening or result in death or hospitalization but may jeopardize the
 participant or may require medical or surgical intervention to prevent one of the other
 outcomes listed in the above definition. These events should usually be considered
 serious.

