10.3.4. Recording and Follow-Up of AE and/or SAE and Product Complaints

AE, SAE, and Product Complaint Recording

When an AE/SAE/product complaint occurs, it is the responsibility of the investigator to review all documentation (for example, hospital progress notes, laboratory reports, and diagnostics reports) related to the event.

The investigator will then record all relevant AE/SAE/product complaint information in the participant's medical records, in accordance with the investigator's normal clinical practice. AE/SAE information is reported on the appropriate eCRF page and product complaint information is reported on the Product Complaint Form.

Note: An event may meet the definition of both a product complaint and an AE/SAE. In such cases, it should be reported as both a product complaint and as an AE/SAE.

It is **not** acceptable for the investigator to send photocopies of the participant's medical records to sponsor or designee in lieu of completion of the eCRF page for AE/SAE and the Product Complaint Form for product complaints.

There may be instances when copies of medical records for certain cases are requested by sponsor or designee. In this case, all participant identifiers, with the exception of the participant number, will be redacted on the copies of the medical records before submission to sponsor or designee.

The investigator will attempt to establish a diagnosis of the event based on signs, symptoms, and/or other clinical information. Whenever possible, the diagnosis (not the individual signs/symptoms) will be documented as the AE/SAE.

Assessment of Intensity

The investigator will make an assessment of intensity for each AE and SAE reported during the study and assign it to one of the following categories:

- Mild: A type of adverse event that is usually transient and may require only minimal treatment or therapeutic intervention. The event does not generally interfere with usual activities of daily living.
- Moderate: A type of adverse event that is usually alleviated with additional specific therapeutic intervention. The event interferes with usual activities of daily living, causing discomfort but poses no significant or permanent risk of harm to the research participant.

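### The amputation/peripheral revascularization AESI is searched by procedure terms, but the protocol's AE rule has sites record the underlying condition, so a low count cannot be read as absence of events

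*SAP*

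**What the plan says.** SAP 3.14.3.1 declares amputation/peripheral revascularization an AESI. On identification it says: "Participants with amputations/peripheral revascularization will be searched using the following MedDRA PTs and summarized". Two terms follow, amputation and peripheral revascularization. The output for the topic is stated as: "A listing of participants with treatment-emergent (TE) events will be provided". For AESIs and special safety topics in general, SAP 3.14.3 adds that "the counts and percentages of participants will be summarized by treatment and PT with decreasing frequency in the tirzepatide arm". SAP Appendix 2 (Section 5.2), which holds the search criteria for several other topics, has no entry for this one.

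Protocol 10.3.1, in its list of events that do not meet the AE definition, has: "Medical or surgical procedure (for example, endoscopy, appendectomy): the condition that leads to the procedure is the AE". Protocol 10.3.4 adds: "Whenever possible, the diagnosis (not the individual signs/symptoms) will be documented as the AE/SAE". Protocol 10.3.2 states: "Hospitalization for elective treatment of a preexisting condition that did not worsen from baseline is not considered an AE".

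Protocol 8.3.3 lists the AESIs in two groups, adjudicated and not adjudicated. The second is introduced by "The following are additional AESI for this program that will not be adjudicated by an external committee". Neither group names amputation or peripheral revascularization. The same section says "The details on the definition of AESI will be provided in SAP" and refers sites to the eCRFs and Section 10.5 for AESI data collection. Section 10.5 does not mention the topic.

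**The concern.** The SAP looks for procedures, while the protocol tells sites to write down the condition that led to the procedure. A site that does as it is told after a leg revascularization would report something like limb ischemia. That term matches neither search term, so the participant would not enter the AESI display.

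What is at stake is how the display is read. The SAP has singled this harm out, in a trial that Protocol 2.2 assumes may include 40% to 50% of participants with T2DM. A listing with no cases, or one, would look reassuring when it might reflect only how events were recorded. Because the rule applies to both arms, the loss would also shrink any difference between them.

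**Working it through.** The plan gives no rate, expected count or precision for this AESI, so there is no figure to reproduce. The check is mainly a comparison of texts, followed by an illustration of how far the count depends on recording.

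**Text comparison**

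1. *Search terms (SAP 3.14.3.1).* Both are procedures. No condition term, SMQ, HLT, procedure form or adjudication source is named.
2. *Data source.* The section does not name the AE database, whereas SAP 3.14.3.3.2 (pancreatitis) and 3.14.3.18 (hypotension) do. The AESI label and the treatment-emergent listing point to AE data. This is an inference, though a strong one.
3. *Recording rule (Protocol 10.3.1 and 10.3.4).* The leading condition, written as a diagnosis, is the AE. Such a record does not match either term.
4. *Elective procedures (Protocol 10.3.2).* Elective hospital treatment of a preexisting condition that has not worsened is not an AE. An elective revascularization could therefore leave no AE record, not even for the condition.
5. *Other capture routes.* None is described in Protocol 8.3.3, Protocol 10.5 or SAP Appendix 2.
6. *Comparison with other procedures.* Protocol 10.5.1.5 names coronary interventions among the nonfatal CV AEs to be adjudicated. The retinopathy list in SAP Appendix 2 includes procedure terms such as vitrectomy, but beside condition terms such as diabetic retinopathy, so a site that records only the condition still produces a hit. SAP 3.14.3.1 has neither safeguard.

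**Illustration of size**

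Inputs: N = 700 (Protocol 1.1). The true incidence p over the study and the share s of procedures written as AE terms are not in the documents. Both are assumptions here, with p from 0.5% to 2% and s from 0 to 100%.

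Formulas: expected participants found = N × p × s; probability of an empty display = (1 − p × s)^N.

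| Share recorded s | Expected, p = 0.5% | P(empty) | Expected, p = 2% | P(empty) |
|---|---|---|---|---|
| 0% | 0 | 1 | 0 | 1 |
| 10% | 700 × 0.005 × 0.10 = 0.35 | 0.705 | 700 × 0.02 × 0.10 = 1.4 | 0.246 |
| 50% | 700 × 0.005 × 0.50 = 1.75 | 0.173 | 700 × 0.02 × 0.50 = 7 | 0.001 |
| 100% | 700 × 0.005 × 1 = 3.5 | 0.030 | 700 × 0.02 × 1 = 14 | <0.001 |

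The same true incidence of 2% could show as no cases, about 1, 7 or 14, depending only on s. If s is equal in both arms, the ratio of expected counts is unchanged, but the counts and their absolute difference are multiplied by s.

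**The case against.** The best counter-argument has four parts.

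*The rule is not applied uniformly.* The protocol itself treats coronary bypass and percutaneous intervention as AEs to be adjudicated, and the SAP searches for several eye procedures by preferred term. The documents therefore expect some procedures to appear as coded terms. This stands. A reader might infer that the display will be close to empty whatever happens, with capture of about 0%. The documents do not support that: it follows only if every site complies perfectly with Protocol 10.3.1. The counter-argument does not remove the gap, however, because peripheral procedures have neither the explicit instruction given to coronary ones nor the condition terms that accompany the eye procedures.

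*The underlying event is still seen.* The limb condition would appear in the TEAE tables (SAP 3.14.1.1). If it led to hospitalization because it was new or had worsened, or needed surgery to prevent permanent impairment, it would be an SAE under Protocol 10.3.2. It would then be in the SAE listing (SAP 3.14.1.4) and in a patient narrative (SAP 3.14.2). This stands, and it rules out a second tempting inference, that limb events would vanish from the report. What is incomplete is the AESI display. The exception is an elective procedure that leaves no AE.

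*Some documents are not available.* Protocol 8.3.3 points to eCRFs and defers AESI definitions to the SAP. The SAP revision summary says safety topics were added to align with a program-level SAP. Either source might contain a capture route. This stands as a limit on certainty. It also means that absence from the 8.3.3 list is not an error in itself; it matters because sites receive no visible instruction.

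*The display is descriptive.* No hypothesis test is specified in SAP 3.14.3.1. This is true and bounds the importance of the point.

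**Conclusion.** The conflict between the two documents is real. To the extent that sites follow Protocol 10.3.1, the two-term search in SAP 3.14.3.1 will miss cases in both arms, and a low or zero count in this display cannot be read as absence of amputations or peripheral revascularizations.

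The size cannot be stated. Neither the event rate nor the recording share is given, and the tabulated figures rest on assumed values for both. The conclusion also assumes that the search runs on AE data, which the treatment-emergent wording supports but the section does not say, and that no capture route exists in the eCRFs or the program-level SAP. It concerns one descriptive safety display and leaves the primary and key secondary analyses untouched.

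**What to change.** 1. In SAP 3.14.3.1 and Appendix 2, keep the two procedure terms and add a supportive search on leading-condition terms, for example limb ischemia, peripheral arterial occlusion, gangrene and diabetic foot. Show these as separate rows, so that a condition is not counted as a procedure.
2. For each supportive hit, check the AE verbatim text and any SAE report for an amputation or revascularization, blinded to treatment and before database lock. Report how many are confirmed.
3. Name the data source for the search in SAP 3.14.3.1, as other sections do.
4. Reconcile SAP 3.14.3.1 with Protocol 10.3.1 and 8.3.3 on how these procedures are recorded. Include elective procedures that Protocol 10.3.2 may leave with no AE, because the added condition terms cannot find those. Simply telling sites to enter procedures as AE terms against 10.3.1 would create a new contradiction, so the passages need to be brought into line with each other.

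The cost is a few appendix terms, a short blinded review of a small set of limb-related AEs, and some less specific hits. No new visits or assessments are needed.

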3.14.3.2. Diabetic Retinopathy Complications

Results of the baseline dilated fundoscopic exam will be summarized by treatment. Any TEAE suspected of worsening retinopathy triggers a follow-up dilated fundoscopic exam. A summary of TEAEs suspected of worsening retinopathy will be summarized by treatment and PT. Severe or serious AEs will be classified as AESI and a listing provided.

A complete list of PTs for inclusion in the above analyses is available in Appendix 2, Section 5.2.

3.14.3.3. Exocrine Pancreas Safety

3.14.3.3.1. Pancreatic Enzyme

Observed pancreatic enzyme data (p-amylase and lipase) will be summarized by treatment and nominal visit.

The counts and percentages of participants with maximum postbaseline pancreatic enzyme value exceeding the following thresholds will be provided by baseline pancreatic enzyme value (\leq upper limit of normal [ULN], > ULN), and postbaseline: \leq 1 \times ULN, (>1 to \leq 3) \times ULN, (>5 to \leq 10) \times ULN, >10 \times ULN.

An MMRM analysis will be used to analyze each pancreatic enzyme with a log-transformed (postbaseline measure/baseline measure) response variable and treatment, nominal visit, and treatment-by-nominal visit interaction as fixed effects.

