10.5.1.2. Pancreatitis

Acute pancreatitis is defined as an AE of interest in all trials with tirzepatide, including this trial.

Acute pancreatitis is an acute inflammatory process of the pancreas that may also involve peripancreatic tissues and/or remote organ systems (Banks and Freeman 2006). The diagnosis of acute pancreatitis requires 2 of the following 3 features:

- abdominal pain, characteristic of acute pancreatitis (generally located in the epigastrium and radiates to the back in approximately half the cases) (Banks and Freeman 2006; Koizumi et al. 2006); the pain is often associated with nausea and vomiting
- serum amylase (total and/or pancreatic) and/or lipase ≥3X ULN, and
- characteristic findings of acute pancreatitis on CT scan or MRI.

If acute pancreatitis is suspected, appropriate laboratory tests (including levels of pancreatic amylase and lipase) should be obtained via the central laboratory (and locally, if needed).

Imaging studies, such as abdominal CT scan with or without contrast, MRI, or gallbladder ultrasound, should be performed. Abdominal ultrasound may be used as an alternative method only if CT and MRI cannot be performed. If laboratory values and/or abdominal imaging support the diagnosis of acute pancreatitis, the participant must discontinue therapy with tirzepatide but will continue in the study. A review of the participant's concomitant medications should be conducted to assess any potential causal relationship with pancreatitis.

Each AE of pancreatitis must be reported. If typical signs and/or symptoms of pancreatitis are present and confirmed by laboratory values (lipase or amylase [total and/or pancreatic]) and imaging studies, the event must be reported as an SAE. For a potential case that does not meet all of these criteria, it is up to the investigator to determine the seriousness of the case (AE or SAE) and the relatedness of the event to study drug(s).

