Each participant will have measurements of p-amylase and lipase (assessed at the central laboratory) as shown on the SoA (Section 1.3) to assess the effects of the investigational doses of tirzepatide on pancreatic enzyme levels. Serial measurements of pancreatic enzymes have limited clinical value for predicting episodes of acute pancreatitis in asymptomatic participants (Nauck et al. 2017; Steinberg et al. 2017a, 2017b). Thus, further diagnostic follow-up of cases of asymptomatic pancreatic hyperenzymemia (lipase and/or pancreatic amylase ≥3X ULN) is not mandated but may be performed based on the investigator's clinical judgment and assessment of the participant's overall clinical condition. Only cases of pancreatic hyperenzymemia that undergo additional diagnostic follow-up and/or are accompanied by symptoms suggestive of pancreatitis will be submitted for adjudication.

All suspected cases of acute or chronic pancreatitis will be adjudicated by an independent clinical endpoint committee. In addition, AEs of severe or serious abdominal pain of unknown etiology will also be submitted to the adjudication committee to assess for possible pancreatitis or other pancreatic disease. Relevant data from participants with acute or chronic pancreatitis and those with severe or serious abdominal pain will be entered into a specifically designed eCRF page. The adjudication committee representative will enter the results of adjudication in a corresponding eCRF page.

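### As printed, the SAP's pancreatic enzyme table has no category for maximum values above 3 and up to 5 × ULN

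*SAP*

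**What the plan says.** SAP 3.14.3.3.1 (Pancreatic Enzyme) plans three things for p-amylase and lipase: observed values by treatment and nominal visit, a repeated-measures model on the log ratio to baseline, and a categorical table. The table is introduced this way: "The counts and percentages of participants with maximum postbaseline pancreatic enzyme value exceeding the following thresholds will be provided". It is split by whether the baseline value was within or above the ULN. The postbaseline categories are up to 1 × ULN and then ">1 to \leq 3) \times ULN, (>5 to \leq 10) \times ULN, >10 \times ULN".

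Protocol 10.5.1.2 (Pancreatitis) uses 3 × ULN twice. It is the enzyme feature among the three from which a diagnosis of acute pancreatitis needs two: "serum amylase (total and/or pancreatic) and/or lipase ≥3X ULN, and". It also defines asymptomatic hyperenzymemia, for which "further diagnostic follow-up of cases of asymptomatic pancreatic hyperenzymemia (lipase and/or pancreatic amylase ≥3X ULN) is not mandated".

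**The concern.** A set of categories for a maximum value should give every measured participant exactly one row. This one does not. Its introduction speaks of exceeding thresholds, but the items are bands, and the two in brackets have upper limits. They cannot be read as cumulative cut-offs that would catch a value of 4 × ULN in a lower row.

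The gap begins at the level that the protocol treats as meaningful. A reader who adds the printed rows above 3 × ULN gets only the participants above 5 × ULN.

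Adjudication need not pick up the rest. Under Protocol 10.5.1.2, hyperenzymemia goes to the committee only if it had additional diagnostic follow-up or came with suggestive symptoms. An asymptomatic participant peaking at 4 × ULN without further work-up would be in neither the adjudicated summary nor a row of this table.

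**Working it through.** The plan states no figure here to reproduce. The check is whether the printed bands cover every possible value, and how they sit against the protocol's level.

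**Inputs.** Bands from SAP 3.14.3.3.1, written as intervals in × ULN: up to 1; (1, 3]; (5, 10]; above 10. Protocol level from 10.5.1.2: at least 3.

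**Step 1: assign test values.**

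| Maximum (× ULN) | SAP category | Meets protocol level of at least 3? |
|---|---|---|
| 1 | up to 1 | no |
| 1.01, 2.99 | (1, 3] | no |
| 3 | (1, 3] | yes |
| 3.01, 4, 4.99, 5 | none | yes |
| 5.01, 10 | (5, 10] | yes |
| 10.01 | above 10 | yes |

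The uncovered interval is (3, 5], with 5 included. The bands meet properly at 1 and at 10, so one band is absent and the rest of the scheme is coherent.

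**Step 2: insert (3, 5] and repeat.** Every test value now falls in exactly one category. A value of exactly 3 stays in (1, 3].

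**Step 3: look for the count elsewhere in the SAP.**
- Section 3.14.5 (Clinical Laboratory Evaluation) gives a shift table by low, normal and high, and a listing of abnormal findings. The shift table does not separate 1.1 from 4 × ULN, and the listing is not a graded count.
- By-visit summaries and the model in 3.14.3.3.1 describe levels over time, not participants in a range.
- Section 3.14.3.3.2 counts pancreatitis events, not enzyme levels.
- For comparison, the ALT and AST displays in 3.14.3.5.2 use cumulative cuts at 1, 3, 5, 10 and 20 × ULN, which leave no gap.

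**Step 4: recover the count by subtraction.** Let N be the number with a postbaseline value in a given arm and baseline stratum. Then

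n(3, 5] = N − n(up to 1) − n(1, 3] − n(5, 10] − n(above 10).

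SAP 3.2 lists sample size among the summary statistics for categorical measures. If the sample size printed is this N, the missing count follows.

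**Step 5: size.** The documents give no frequency for this range. With about 350 participants per arm (Protocol 9.2), each 1% peaking in it is 350 × 0.01 = 3.5 participants without a row. On assumed frequencies of 2% and 6%, that is 350 × 0.02 = 7 and 350 × 0.06 = 21 per arm. These show scale only and are not estimates.

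**The case against.** The strongest objection is that the band may have been lost when the PDF was read. Only one item, nearly identical to its neighbours, is absent, and category limits look altered elsewhere in the same text. SAP 3.14.3.14.1 shows overlapping calcitonin bands. SAP 3.15.2.1 shows BMI bands that overlap at 35 and 40, where 3.9 and 3.15.1 have clean cuts. This stands as a reason to check the source and to lower confidence. It does not dispose of the point: those cases involve a changed sign, here a whole band is missing, and the sentence is continuous with no gap or redaction mark.

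The second objection is that little depends on the table. Protocol 10.5.1.2 itself says serial enzyme values have limited predictive value in people without symptoms, and further work-up at this level is not required ("lipase and/or pancreatic amylase ≥3X ULN) is not mandated"). The adverse event of special interest is adjudication-confirmed pancreatitis, which does not use these bands. That is correct, and it keeps the point minor.

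Three stronger readings are tempting, and the documents do not support them:
- A reader might infer that the SAP has no other categorical display of these enzymes. The shift table and abnormal-findings listing in 3.14.5 cover all safety laboratory data. What is true is that no other display is graded by multiples of ULN.
- A reader might infer that the table cannot show whether treatment moves participants past 3 × ULN. If N is printed, the number above 3 × ULN is N minus the two lowest rows, by arm and baseline stratum.
- A reader might infer that placing exactly 3 × ULN in the lower band is a material misclassification. It differs from the protocol's inequality, but matters little for a continuous laboratory value.

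**Conclusion.** The concern holds in limited form. On the text as it reads, participants whose maximum lies above 3 and up to 5 × ULN have no row in the SAP's only ULN-graded display of pancreatic enzymes, and the gap starts at the protocol's own level. The rows need not add to the number measured, and the omitted count has to be worked out as a residual.

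The consequence stops at that descriptive safety table. Nothing in the primary, key secondary or adjudicated results changes. The number of participants affected cannot be stated from the documents. The conclusion assumes that the printed list is what the SAP actually contains. Severity is minor and confidence moderate.

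**What to change.** First check the sentence in the source PDF of the SAP. If the band is there, no change is needed. If it is not, insert a category for values above 3 and up to 5 × ULN, which makes the list exhaustive under the convention it already uses. The boundaries at 5 and 10 × ULN need no change.

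Optionally, add one row for any postbaseline value of at least 3 × ULN, so that the table gives the protocol's level directly and the handling of exactly 3 is settled.

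The cost is one line of SAP text and a change to the table shell. No new data are needed, and clinical management is not affected.
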